### 3 Background and Rationale

#### 3.1 Introduction

Lenalidomide, a thalidomide analog, belongs to a proprietary class of Celgene compounds called immunomodulatory drugs (IMiDs®). IMiDs® have both immunomodulatory and anti-angiogenic properties which could confer antitumor and antimetastatic effects.

Although the exact antitumor mechanism of action of lenalidomide is unknown, a number of mechanisms are postulated to be responsible for lenalidomide's activity against multiple myeloma. Lenalidomide has direct activity against multiple myeloma and induces apoptosis or G1growth arrest in multiple myeloma cell lines and in multiple myeloma cells of patients resistant to melphalan, doxorubicin and dexamethasone . Lenalidomide, a thalidomide analog, has been demonstrated to possess anti-angiogenic activity through inhibition of bFGF, VEGF and TNF-alpha induced endothelial cell migration, due at least in part to inhibition of Akt phosphorylation response to bFGF. In addition, lenalidomide has a variety of immunomodulatory effects. Lenalidomide stimulates T cell proliferation, and the production of IL-2, IL-10 and IFN-gamma, inhibits IL-1 beta and IL-6 and modulates IL-12 production. Upregulation of T cell derived IL-2 production is achieved at least in part through increased AP-1 activity. The increased level of these circulating cytokines augment natural killer cell number and function, and enhance natural killer cell activity to yield an increase in multiple myeloma cell lysis .

#### 3.2 Clinical experience in multiple myeloma with lenalidomide

In 2 phase I studies in multiple myeloma, a total of 41 patients have been treated with lenalidomide. In one study at the University of Arkansas, 15 patients who relapsed or were refractory to high dose melphalan therapy with stem cell transplant were treated for 4 weeks in an open-label safety study and were permitted to continue therapy in an extension phase of the trial. Patient cohorts were treated at the following daily doses: 5mg, 10mg, 25mg, and 50mg . In a similar study at the Dana Farber Cancer Institute, 27 patients with rapidly advancing refractory multiple myeloma were enrolled .

Anti-myeloma activity was observed in each of these 2 phase I studies. Decreases in neutrophil and platelet counts were the dose-limiting toxicities associated with lenalidomide. The maximum tolerated dose (MTD) was not

reached within 28 days. Due to dose modifications associated with myelosuppression observed beyond Day 28 at the 25mg and 50mg daily dose levels, the dose schedule most widely used in future studies has been lenalidomide 25 mg on Days 1-21, repeated every 28 days.

Pharmacokinetic analyses were performed on 15 multiple myeloma patients treated in the phase I studies. Absorption was found to be rapid on both Day 1 and Day 28 with time to maximum blood levels ranging from 0.7 to 2.0 hours at all dose levels (5mg, 10mg, 25mg, and 50mg). Plasma lenalidomide declined in a monophasic manner with elimination half-life ranging from 2.8 to 6.1 hours on both Day 1 and 28 at all 4 doses. No plasma accumulation was observed with multiple daily dosing. Peak and overall plasma concentrations were dose proportional over the dosing range of 5mg to 50mg .

A multicenter, randomized, phase II trial compared 2 syncopated dose schedules of lenalidomide (15 mg B.D. vs. 30 mg O.D.) used alone or in combination with dexamethasone in the treatment of relapsed or refractory multiple myeloma. All patients were treated on Days 1-21 of a 28-day cycle. Patients treated with 15mg BID experienced more myelosuppression and dose reductions compared with patients treated with 30mg daily. Anti-myeloma activity was observed with each dose and schedule of single agent lenalidomide. The addition of dexamethasone to lenalidomide yielded responses in some patients who had not responded to lenalidomide alone .

Celgene Corporation sponsored 2 multicenter, randomized, double-blinded, placebo-controlled phase III trials [1 U.S. (MM-009) and 1 international (MM-010)] in patients with relapsed or refractory multiple myeloma . More than 350 patients were enrolled into each of these studies. All patients had to be considered sensitive to dexamethasone and were treated with dexamethasone 40mg daily on Days 1-4, 9-12 and 17-20. In addition to receiving dexamethasone, patients were randomized to lenalidomide 25mg or placebo each given daily on Days 1-21. Cycles were repeated every 28 days. After 4 cycles, there was a predetermined reduction of the dexamethasone dose to 40mg daily on Days 1-4 repeated every 28 days. In both studies, a pre-specified interim analysis conducted by an Independent Data Monitoring Committee demonstrated that subjects receiving the combination of lenalidomide (Len) plus dexamethasone (Dex) had significantly longer times to progression and higher response rates (D 27% vs. 2D 61%,  $p < 0.001$ ) than those treated with single-agent dexamethasone. These studies led to the FDA approval of lenalidomide in combination with dexamethasone for the treatment of multiple myeloma in

patients that have received at least one prior therapy. Based on an excellent efficacy in relapsed patients, a recent phase II trial utilizing lenalidomide plus dexamethasone for newly diagnosed multiple myeloma patients was recently reported by the Mayo Clinic. Lenalidomide was given orally 25 mg daily on days 1-21 of a 28-day cycle. Dexamethasone was given orally 40 mg daily on days 1-4, 9-12, 17-20 of each cycle. Objective response was defined as a decrease in serum monoclonal protein by 50% or greater and a decrease in urine M protein by at least 90% or to a level less than 200 mg/24 hours, confirmed by two consecutive determinations at least 4 weeks apart. Thirty-one of 34 (91%) patients achieved an objective response, including 2 (6%) achieving complete response (CR), and 11 (32%) meeting criteria for both very good partial response and near complete response, resulting in an overall objective response rate of 91%. Of the 3 remaining patients not achieving an objective response, two had minor response (MR) and one stable disease. Forty-seven percent of patients experienced grade 3 or higher non-hematologic toxicity, most commonly fatigue (15%), muscle weakness (6%), anxiety (6%), pneumonitis (6%) and rash (6%). Revlimid®/dexamethasone is a highly active regimen with manageable side-effects in the treatment of newly diagnosed myeloma.(18)

### 3.3 Rationale

The primary rationale is to utilize Revlimid at dose that will be well tolerated and effective. We propose to use the need for dose reduction as a criterion to judge tolerability from various causes. In the veteran population which predominantly is in the older age category with number of co-morbidities, a lower dose regimen may be safer and advantageous. In a recent multi-institutional study, the 009 and 010 studies, patients were randomized to receive Revlimid with dexamethasone versus dexamethasone alone. A logistic regression was performed using dose reduction (i.e., whether or not having any lenalidomide dose reduction as the dependent variable). Treatment-emergent neutropenia and thrombocytopenia were the causes of the majority of dose reductions. Predictors analyzed included: age, prior transplant (yes vs. no), high vs. low risk (disease stage variable), previous thalidomide exposure (yes vs. no), previous lines of therapy (<=2 vs. 3+), prior medical history of neutropenia or thrombocytopenia. Among the 353 patients in the Revlimid/Dexamethasone groups, 131 (37.1%) had at least one dose reduction of Revlimid. Age, whether used as a continuous variable or dichotomized one (<=65 vs. 66+), was the single significant predictor for dose reduction; 46% of the patients aged 66 or older required at least one dose reduction, as compared to 31% of the patients aged 65 or younger. Of

interest, when the elderly population was specifically examined, the outcomes were similar for response rate, time to progression and overall survival than the younger group, suggesting that dose reduction had no significant effect on efficacy.

### **3.3.1 INDICATIONS AND USAGE:**

Revlimid® is approved in combination with dexamethasone for the treatment of patients with multiple myeloma that have received at least one prior therapy. Revlimid® (lenalidomide) is also indicated for the treatment of patients with transfusion-dependent anemia due to Low- or Intermediate-1-risk myelodysplastic syndromes associated with a deletion 5q cytogenetic abnormality with or without additional cytogenetic abnormalities.

### **3.4 Adverse Events**

Most frequently reported adverse events reported during clinical studies with lenalidomide in oncologic and non-oncologic indications, regardless of presumed relationship to study medication include: anemia, neutropenia, thrombocytopenia and pancytopenia, abdominal pain, nausea, vomiting and diarrhea, dehydration, rash, itching, infections, sepsis, pneumonia, UTI, Upper respiratory infection, atrial fibrillation, congestive heart failure, myocardial infarction, chest pain, weakness, hypotension, hypercalcemia, hyperglycemia, back pain, bone pain, generalized pain, dizziness, mental status changes, syncope, renal failure, dyspnea, pleural effusion, pulmonary embolism, deep vein thrombosis, CVA, convulsions, spinal cord compression, disease progression, death not specified and fractures. Tumor flare reaction (TFR) has been reported frequently in CLL patients treated with lenalidomide. Tumor lysis syndrome (TLS) has been reported in CLL patients treated with lenalidomide. Precautions must be taken to prevent TLS including proper selection of patients with regard to renal function, correction of electrolyte abnormalities, and TLS prophylaxis and monitoring. Lenalidomide has been shown to increase the level of digoxin in the blood in some patients.

#### **Second new cancers**

According to researchers, patients with cancer have a higher risk of developing a second new cancer when compared to people without cancer. In clinical studies of newly diagnosed multiple myeloma, a higher number of second cancers were reported in patients treated with induction therapy (treatment as first step to reducing number of cancer cells) and/or bone marrow transplant then lenalidomide for a long period of time compared to patients treated with induction therapy and/or bone marrow transplant then placebo (a capsule containing no lenalidomide). Patients should make their doctors aware of their medical history

and any concerns they may have regarding their own increased risk of other cancers.

Complete and updated adverse events are available in the Investigational Drug Brochure and the IND Safety Letters.

## **4 Study Objectives and Endpoints**

### **4.1 Objectives**

#### **4.1.1 Primary objectives**

- Evaluate the frequency of dose reductions in two different lenalidomide dose regimens.

#### **4.1.2 Secondary study objectives**

- Evaluate efficacy of two different lenalidomide dose regimens in patients with multiple myeloma using the EBMT and IMWG criteria.
- Evaluate the duration of response of 15 mg lenalidomide and 25 mg lenalidomide when used in combination with low-dose dexamethasone
- Evaluate the safety of 15 mg and 25 mg lenalidomide regimens when in combination with dexamethasone
- Explore the blood and cellular levels of angiogenic factors, cytokines, and adhesion molecules

### **4.2 Endpoints**

#### **4.2.1 Primary Endpoint**

- Type, frequency, severity and timing of adverse events and their relationship to combination therapy with lenalidomide plus dexamethasone.

#### **4.2.2 Secondary Endpoints**

- Duration of M-Protein response during combination therapy with Lenalidomide plus dexamethasone
- Confirmed M-Protein response
- Expression of angiogenic factors, cytokines, adhesion molecules, and myeloma biomarker expression

## 5 Investigational Plan

### 5.1 Overall design

This is a multi-center, controlled, open-label, randomized (1:1) parallel group study intended to select the dose regimen with the most promising efficacy of Lenalidomide, when used in combination with dexamethasone.

[figure not shown]
Subjects will receive either oral Lenalidomide 25 mg once daily for days 1-21 out of a 28 cycle or Lenalidomide 15 mg once daily for 1-21 of a 28 day cycle. Subjects will also receive 40 mg of dexamethasone once a week (Days 1, 8, 15 and 22) with a dose reduction on the same schedule if the patient cannot tolerate the higher dose of dexamethasone ([refer to Section 5.5.3](#)). ASA (81 or 325 mg) will be given orally for anticoagulation prophylaxis. If patient has progressive disease after 2nd cycle, then the patient will be taken off the study. If at least a minimal response (MR) has not resulted after cycle 4, then the patient will be taken off the study. Subjects who continue to show evidence of myeloma response will remain on the study and will be evaluated every 4 weeks for response/progression.

#### 5.1.1 Investigational Drug

##### 5.1.1.1 Lenalidomide Description

REVLIMID® (lenalidomide), a thalidomide analogue, is an immunomodulatory agent with anti-angiogenic properties. The chemical name is 3-(4-amino-1-oxo 1,3-dihydro-2*H*-isoindol-2-yl) piperidine-2,6-dione and it has the following chemical structure:

###### 5.1.1.1.1.1 Chemical Structure of Lenalidomide

3-(4-amino-1-oxo 1,3-dihydro-2*H*-isoindol-2-yl) piperidine-2,6-dione

The empirical formula for lenalidomide is C13H13N3O3, and the gram molecular weight is 259.3.

Lenalidomide is an off-white to pale-yellow solid powder. It is soluble in organic solvent/water mixtures, and buffered aqueous solvents. Lenalidomide is more soluble in organic solvents and low pH solutions. Solubility was significantly lower in less acidic buffers, ranging from about 0.4 to 0.5 mg/ml. Lenalidomide has an asymmetric carbon atom and can exist as the optically active forms S(-) and R(+), and is produced as a racemic mixture with a net optical rotation of zero.

REVLIMID® (lenalidomide) is available in 5 mg and 25 mg capsules for oral administration.

#### 5.1.1.2 CLINICAL PHARMACOLOGY

##### **Mechanism of Action:**

The mechanism of action of lenalidomide remains to be fully characterized. Lenalidomide possesses immunomodulatory and antiangiogenic properties. Lenalidomide inhibited the secretion of pro-inflammatory cytokines and increased the secretion of anti-inflammatory cytokines from peripheral blood mononuclear cells. Lenalidomide inhibited cell proliferation with varying effectiveness (IC50s) in some but not all cell lines. Of cell lines tested, lenalidomide was effective in inhibiting growth of Namalwa cells (a human B cell lymphoma cell line with a deletion of one chromosome 5) but was much less effective in inhibiting growth of KG-1 cells (human myeloblastic cell line, also with a deletion of one chromosome 5) and other cell lines without chromosome 5 deletions. Lenalidomide inhibited the expression of cyclooxygenase-2 (COX-2) but not COX-1 in vitro.

##### **5.1.1.3 Pharmacokinetics and Drug Metabolism:**

##### **Absorption:**

Lenalidomide, in healthy volunteers, is rapidly absorbed following oral administration with maximum plasma concentrations occurring between 0.625 and 1.5 hours post-dose. Co-administration with food does not alter the extent of absorption (AUC) but does reduce the maximal plasma concentration (Cmax) by 36%. The pharmacokinetic disposition of lenalidomide is linear. Cmax and AUC increase proportionately with increases in dose. Multiple dosing at the recommended dose-regimen does not result in drug accumulation.

Pharmacokinetic sampling in myelodysplastic syndrome (MDS) patients was not performed. In multiple myeloma patients maximum plasma concentrations occurred between 0.5 and 4.0 hours post-dose both on Days 1 and 28. AUC and Cmax values increase proportionally with dose following single and multiple doses. Exposure (AUC) in multiple myeloma patients is 57% higher than in healthy male volunteers.

##### **Pharmacokinetic Parameters:**

##### **Distribution:**

In vitro (C)-lenalidomide binding to plasma proteins is approximately 30%.

##### **Metabolism and Excretion:**

The metabolic profile of lenalidomide in humans has not been studied. In healthy volunteers, approximately two-thirds of lenalidomide is eliminated unchanged

through urinary excretion. The process exceeds the glomerular filtration rate and therefore is partially or entirely active. Half-life of elimination is approximately 3 hours.

#### **5.1.1.4 Supplier(s)**

Celgene Corporation will supply Revlimid® (lenalidomide) to study participants at no charge through the RevAssist® program.

#### **5.1.1.5 Dosage form**

Lenalidomide will be supplied as 5 mg and 25 mg capsules for oral administration.

#### **5.1.1.6 Packaging**

Lenalidomide will be shipped to the pharmacy at the study site in individual bottles. Bottles will contain a sufficient number of capsules to last for one cycle of dosing. Study drug must be dispensed in the original packaging with the label clearly visible. **Only enough lenalidomide for 1 cycle of therapy may be provided to the patient each cycle.**

#### **5.1.1.7 Labeling**

Lenalidomide investigational supplies are dispensed to the patients in individual bottles of capsules. Each bottle will identify the contents as study medication. In addition, the label will bear Celgene's name, quantity contained and the standard caution statement as follows: Caution: New drug - Limited by Federal law to investigational use. The study drug label must be clearly visible. For appropriate drug accountability, it is recommended that the institution mark each bottle with the institutional protocol number or Celgene tracking number (**RV-PI-MM-0345**) upon receipt. Additional labels must not cover the Celgene label.

#### **5.1.1.8 Receipt of study drug**

The Investigator or designee is responsible for taking an inventory of each shipment of study drug received, and comparing it with the accompanying study drug accountability form. The Investigator will verify the accuracy of the information on the form, sign and date it, retain a copy in the study file, and return a copy to Celgene or its representative.

#### **5.1.1.9 Storage**

At the study site, all investigational study drugs will be stored in a locked, safe area to prevent unauthorized access.

The study drug should be stored at room temperature away from direct sunlight and protected from excessive heat and cold.

#### 5.1.1.10 Unused study drug supplies

Celgene will instruct the Investigator on the return or destruction of unused study drug. If any study drug is lost or damaged, its disposition should be documented in the source documents. Study drug supplies will be retained at the clinical site pending instructions for disposition by Celgene. Patients will be instructed to return empty bottles or unused capsules.

#### 5.1.1.11 Drug dispensing requirements

Lenalidomide (Revlimid®) will be provided to research subjects for the duration of their participation in this trial at no charge to them or their insurance providers. Lenalidomide will be provided in accordance with the RevAssist® program of Celgene Corporation. Per standard RevAssist® requirements all physicians who prescribe lenalidomide for research subjects enrolled into this trial, and all research subjects enrolled into this trial, must be registered in and must comply with all requirements of the RevAssist® program. Prescriptions must be filled within 7 days for females of childbearing potential and 14 days for all other risk categories. Drug will be shipped on a per patient basis by the contract pharmacy to the clinic sites. **Only enough lenalidomide for one cycle of therapy will be supplied to the patient each cycle.**

#### Pregnancy Testing

Refer to Appendix A: Risks of Fetal Exposure, Pregnancy Testing Guidelines and Acceptable Birth Control Methods). All counseling will be done through RevAssist®.

## 5.2 Screening and Eligibility

The Investigator is responsible for keeping a record of all subjects who sign an Informed Consent Form for entry into the study. All subjects will be screened for eligibility. Screening procedures are outlined in Section 2, Schedule of Study Assessments and unless otherwise specified, must take place within 14 days prior to initiation of therapy.

Approximately 80 of subjects with active multiple myeloma will be screened for enrollment and must meet the eligibility criteria below.

### 5.2.1 Inclusion Criteria

Subjects must meet the following inclusion/exclusion criteria to be eligible for the study.

**Inclusion criteria**

**5.2.1.1 Subject was previously diagnosed with multiple myeloma based on standard diagnostic criteria as follows.**

**Diagnostic Criteria for Multiple Myeloma, Myeloma Variants, and Monoclonal Gammopathy of Unknown Significance****Monoclonal gammopathy of undetermined significance (MGUS)**

- M-protein in serum <30 g/l
- Bone marrow clonal plasma cells <10%
- No evidence of other B-cell proliferative disorders
- No myeloma related organ or tissue impairment (no end organ damage, including bone lesions)

**Asymptomatic myeloma (smoldering myeloma).**

- M-protein in serum  $\geq 30$  g/l and/or
- Bone marrow clonal plasma cells  $\geq 10\%$
- No myeloma related organ or tissue impairment (no end organ damage, including bone lesions) or symptoms

**Symptomatic multiple myeloma.**

- M-protein in serum and/or urine
- Bone marrow (clonal) plasma cells\* or plasmacytoma
- Myeloma related organ or tissue impairment (end organ damage, including bone lesions)
- \*If flow cytometry is performed, most plasma cells (> 90%) will show a 'neoplastic' phenotype.

**Non-secretory myeloma.**

- No M-protein in serum and/or urine with immunofixation
- Bone marrow clonal plasmacytosis  $\geq 10\%$  or plasmacytoma
- Myeloma-related organ or tissue impairment (end organ damage, including bone lesions)

**Solitary plasmacytoma of bone.**

- No M-protein in serum and/or urine\*
- Single area of bone destruction due to clonal plasma cells
- Bone marrow not consistent with multiple myeloma
- Normal skeletal survey (and MRI of spine and pelvis if done)
- No related organ or tissue impairment (no end organ damage other than solitary bone lesion)\*
- \*A small M-component may sometimes be present.

---

**Myeloma-related organ or tissue impairment (end organ damage) (ROTI)**

- \*Calcium levels increased: serum calcium > 0.25 mmol/l above the upper limit of normal or > 2.75 mmol/l
- \*Renal insufficiency: creatinine >173 mmol/l

- \*Anemia: haemoglobin 2 g/dl below the lower limit of normal or haemoglobin <10 g/dl
- \*Bone lesions: lytic lesions or osteoporosis with compression fractures (MRI or CT may clarify)

**Other: symptomatic hyperviscosity, amyloidosis, recurrent bacterial infections (> 2 episodes in 12 months)**

**5.2.1.1** Patients must have relapsed or refractory disease (refractory is defined as progression during treatment or within 60 days after the completion of treatment) requiring 2nd or 3rd line therapy (see Appendix C)

**5.2.1.2** Patients may have received lenalidomide and/or dexamethasone

**5.2.1.3** Patients with measurable disease defined as:

- Serum monoclonal protein > 0.5 g/dL and/or 0.2 g/24hr urine light chain excretion
- Patients with lower M-protein values or non-secretory myeloma will be eligible if measurable disease can be established, such as serum Freelite™ chain ratio > 5x normal limit, measurable soft tissue plasmacytoma > 2 cm by either physical exam and/or applicable radiographs (i.e. MRI, CT-scan) and/or bone marrow involvement > 30%

- 5.2.1.4** Age  $\geq 18$  years at the time of signing the informed consent form.
- 5.2.1.5** All necessary baseline studies for determining eligibility must be obtained within 14 days prior to enrollment. Serum pregnancy tests (sensitivity of at least 50 mIU/mL), for females of childbearing potential (WCBP) must be completed. The first test must be performed within 10-14 days, and the second test within 24 hours prior to initiation of lenalidomide.
- 5.2.1.6** Pre-study ECOG performance status 0-2. Patients with lower performance status based solely on bone pain will be eligible.
- 5.2.1.7** Patients must have adequate liver functions: AST and ALT  $\leq 3x$  upper limit of normal, alkaline phosphatase  $\leq 3.0x$  upper limit of normal, except if attributed to tumor, and bilirubin  $\leq 2 x$  upper limit of normal.
- 5.2.1.8** Patients must have amylase  $\leq 2.5x$  upper limit of normal
- 5.2.1.9** All study participants must be registered into the mandatory RevAssist® program, and be willing and able to comply with the requirements of RevAssist®.
- 5.2.1.10** Subject must be able to adhere to the study visit schedule and other protocol requirements
- 5.2.1.11** Subject must understand and voluntarily sign an informed consent document.
- 5.2.1.12** Females of childbearing potential (FCBP)† must have a negative serum or urine pregnancy test with a sensitivity of at least 50 mIU/mL 10 – 14 days prior to and again within 24 hours of starting Lenalidomide for Cycle 1 (prescriptions must be filled within 7 days as required by RevAssist) and must either commit to continued abstinence from heterosexual intercourse or begin TWO acceptable methods of birth control, one highly effective method and one additional effective method AT THE SAME TIME, at least 28 days before she starts taking lenalidomide. FCBP must also agree to ongoing pregnancy testing. Men must agree to use a latex condom during sexual contact with a FCBP even if they have had a successful vasectomy. All patients must be counseled at a minimum of every 28 days about pregnancy precautions and risks of fetal exposure through the RevAssist® program. See Appendix A: Risks of Fetal Exposure, Pregnancy Testing Guidelines and Acceptable Birth Control Methods. All counseling will be done through RevAssist®.
- 5.2.1.13** Able to take aspirin (81 or 325 mg) daily as prophylactic anticoagulation. Patients intolerant to ASA may use low molecular weight heparin. Lovenox is recommended. Coumadin will be allowed provided the patient is fully anticoagulate with INR 2.0 to 2.5.

---

† A female of childbearing potential is a sexually mature woman who: 1) has not undergone a hysterectomy or bilateral oophorectomy; or 2) has not been naturally postmenopausal for at least 24 consecutive months (i.e., has had menses at any time in the preceding 24 consecutive months).

**5.2.1.14** Patients may receive a bisphosphonate.

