## 5.7 Discontinuation of Study Treatment

Treatment will continue until the occurrence of any of the following events.

- Disease progression as defined in Appendix C
- Adverse event(s) that, in the judgment of the Investigator, may cause severe or permanent harm or which rule out continuation of the treatment regimen.
- Discontinuation of lenalidomide for any reason.
- Major violation of the study protocol.
- Withdrawal of consent
- Lost to follow up
- Death
- Pregnancy
- Patient requests to be removed from study

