**Criteria for Response**

Requires all of the following:

- Disappearance of the original monoclonal protein from the blood and urine on at least two determinations for a minimum of six weeks by immunofixation studies
- < 5% plasma cells in the bone marrow on at least one determination
- No increase in the size or number of lytic bone lesions (development of a compression fracture does not exclude response)
- Disappearance of soft tissue plasmacytomas for at least six weeks.

Near CR

- Requires all of above except immunofixation remains positive
- Or normal FLC ratio

Partial Response (PR)

Requires all of the following:

- $\geq 50\%$  reduction in the level of serum monoclonal protein for at least two determinations six weeks apart
- If present, reduction in 24-hour urinary light chain excretion by either  $\geq 90\%$  or to < 200 mg for at least two determinations six weeks apart
- $\geq 50\%$  reduction in the size of soft tissue plasmacytomas (by clinical or radiographic examination) for at least six weeks
- No increase in size or number of lytic bone lesions (development of compression fracture does not exclude response)
- If the serum and urine M-protein are unmeasurable a  $\geq 50\%$  decrease in the difference between involved and uninvolved FLC levels is required in place of the M-protein criteria

Minimal Response (MR)

Requires all of the following:

- $\geq 25\%$  to  $\leq 49\%$  reduction in the level of serum monoclonal protein for at least two determinations six weeks apart
- If present, a 50 to 89% reduction in 24 hour light chain excretion, which still exceeds 200 mg/24hr, for at least two determinations six weeks apart.
- For patients with non-secretory myeloma only, a 25 to 49% reduction in plasma cells in the bone marrow for a minimum of six weeks
- no increase in size or number of lytic bone lesions (development of compression fracture does not exclude response)

Stable Disease

Not meeting the criteria for CR, PR or PD

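### Appendix C gives no route to minimal response through FLC or a soft tissue plasmacytoma, so the cycle 4 rule can remove patients admitted on those measures while that disease is shrinking

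*Combined protocol and SAP*

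**What the plan says.** **Eligibility.** Section 5.2.1.3 normally asks for serum monoclonal protein above 0.5 g/dL and/or 0.2 g/24hr of urine light chain. Patients below that, or with non-secretory disease, may enter on a serum FLC ratio above 5 times the normal limit, or on "measurable soft tissue plasmacytoma > 2 cm by either physical exam and/or applicable radiographs (i.e. MRI, CT-scan) and/or bone marrow involvement > 30" per cent.

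**Partial response.** Appendix C has a plasmacytoma line, a 50% or greater "reduction in the size of soft tissue plasmacytomas (by clinical or radiographic examination) for at least six weeks". It also has an FLC substitute for unmeasurable M-protein: a 50% or greater "decrease in the difference between involved and uninvolved FLC levels is required in place of the M-protein criteria".

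**Minimal response.** Appendix C lists serum M-protein, urine light chain, lytic lesions and one marrow line: "For patients with non-secretory myeloma only, a 25 to 49% reduction in plasma cells in the bone marrow for a minimum of six weeks". It mentions neither FLC nor plasmacytoma size.

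**Stable disease.** This is the residual category: "Not meeting the criteria for CR, PR or PD".

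**Consequence.** Section 5.1 states: "If at least a minimal response (MR) has not resulted after cycle 4, then the patient will be taken off the study". The synopsis and footnote 10 of the Section 2 schedule repeat the rule.

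**The concern.** MR is more than a descriptive category here, because it decides whether treatment continues past cycle 4. A patient followed by serum M-protein who has a 30% fall stays on. A patient followed by FLC or by a plasmacytoma who has the same 30% fall has no MR line that recognises it. The documents give no reason for treating the two differently.

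At stake are continued treatment for individual patients and consistent decisions across sites in an open-label multi-center trial. Secondary efficacy is also affected, since a patient removed at cycle 4 has no chance of a later PR on study. Section 10.3 defines the primary outcome as any dose reduction, which does not depend on response category.

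**Working it through.** The plan gives no figure on this point. Its sizing figure in Section 10.5 (81.6% power, 50% versus 20%, 40 per arm) reproduces at 81.55% with the pooled normal approximation, and this issue does not change it.

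**1. Qualifying measures against Appendix C**

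| Only measurable disease | CR | PR | MR |
|---|---|---|---|
| Serum FLC | yes (closing note) | yes | no |
| Soft tissue plasmacytoma | yes | yes | no |
| Marrow, non-secretory | yes | no | yes |

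Patients whose M-protein is low but quantifiable can be scored on the serum line, since Appendix C sets no minimum baseline. They are not part of this point.

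**2. Is there another way to MR?** Suppose inapplicable MR lines are waived.

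- The serum line drops out when M-protein cannot be quantified.
- The urine line requires a residual above 200 mg/24hr, so a patient who enters at or below 0.2 g/24hr cannot meet it.
- The lytic-lesion line only requires no worsening.
- The marrow line remains, for non-secretory patients only. Section 5.2.1.1 defines these as having no M-protein on immunofixation.

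The gap is therefore strict for immunofixation-positive but unquantifiable disease, and for plasmacytoma patients with little marrow disease. For other non-secretory patients it is practical: they need a marrow fall held six weeks, and footnote 9 of the schedule allows on-study marrow only when clinically indicated or to confirm CR.

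**3. Upper bound on removals.** Let m be the number of FLC-only plus plasmacytoma-only patients, and q the share whose best fall by week 16 is 25–49%. Neither is in the documents. The one anchor for q is Section 3.2, in newly diagnosed patients: "Of the 3 remaining patients not achieving an objective response, two had minor response (MR) and one stable disease". That is 2/34 = 5.9%. The upper value of 20%, and m = 4 or 8 of 80, are assumptions.

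Expected removals ≤ m × q. Chance of at least one ≤ 1 − (1 − q)^m.

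| m | q | m × q | Chance of at least one |
|---|---|---|---|
| 4 | 5.9% | 0.24 | 22% |
| 4 | 20% | 0.80 | 59% |
| 8 | 5.9% | 0.47 | 38% |
| 8 | 20% | 1.60 | 83% |

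These are upper bounds because they give no credit for the marrow route in step 2.

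**4. Secondary note: PR has no marrow line.** A marrow-only patient whose plasma cells fall by 50% or more, short of CR, cannot count toward the objective response rate (ORR). The expected loss per such patient in an arm of 40 is (p − c)/40, where p is the true ORR and c the chance of CR. Take p = 61%, the Section 3.2 rate from the phase III trials, which used a different dexamethasone schedule.

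- c = 0: 0.61/40 = 1.5 points.
- c = 6% (the 2 of 34 CRs in Section 3.2): 0.55/40 = 1.4 points.
- c = 25% (assumed): 0.36/40 = 0.9 points.
- c = 38% (adding the 11 of 34 with very good partial or near-complete response, so 13/34): 0.23/40 = 0.6 points.

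Section 10.3 asks whether a one-sided 95% lower limit exceeds 45%. By the exact method this needs 24/40 (limit 45.8%; 23/40 gives 43.3%). At p = 61% the chance of reaching it is 62% with no marrow-only patients in the arm. With two, it is 48% at c = 6%, 53% at c = 25% and 56% at c = 38%. Pooled over 80, where 44 are needed, it is 89% with none, and 83% (c = 6%) to 87% (c = 38%) with two.

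**The case against.** The strongest reply is that most patients left without quantifiable M-protein are non-secretory, and MR has a marrow line for them. MR needs to be reachable; it does not have to be reached through the measure that qualified the patient. That stands, and it is why m × q is only an upper bound. It does not close the gap: the line excludes immunofixation-positive patients, does little for plasmacytoma patients with little marrow disease, and relies on marrow samples that are not scheduled.

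A second reply is that Section 7 has response evaluated by the EBMT and IMWG criteria and treats Appendix C as guidance on interpreting them. Those sources may fill the gap. The documents do not show whether they do, and Appendix C is the text sites are sent to.

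A third is that sites will use judgement. Section 5.1 keeps subjects who continue to show myeloma response. Section 5.7, to which the synopsis refers for the rule, opens with "Treatment will continue until the occurrence of any of the following events" and does not list failure to reach MR. Stable disease, read literally, does not exclude MR either. All this is true, but it makes inconsistent decisions more likely, and the cycle 4 rule still asks for MR by name.

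A reader might also infer more than the text supports:

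- **Every FLC-only or plasmacytoma-only patient with a 25–49% fall is removed.** The marrow route means some need not be.
- **Marrow-only patients are removed too.** A marrow fall of 50% or more is sensibly at least MR.
- **PR is out of reach for plasmacytoma-only disease.** The text is unclear on this point: the FLC substitute does not say what applies when FLC is uninformative.
- **The ORR loss is close to 1.4–1.5 points per marrow-only patient.** That takes a CR chance of 0–6%. A positive immunofixation cannot hold a non-secretory patient below CR, so higher values are plausible and the loss is smaller.

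**Conclusion.** The concern holds in a limited form. Two qualifying measures in Section 5.2.1.3 have no counterpart in the MR definition, and MR decides whether treatment continues after cycle 4. Following the text can therefore take a patient off treatment while the qualifying disease is shrinking by 25–49%.

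The number affected is unknown and may be zero. Under the assumed m and q, 0.2–1.6 removals is a ceiling. The effect is on retention and secondary efficacy. The documents do not support reading this as a bias in the primary comparison: dose reduction is not defined by response, and the rule is the same in both arms.

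The missing PR marrow line is a side note, at about 0.6–1.5 ORR points per marrow-only patient in an arm of 40, depending on the CR chance assumed. Section 10.3 attaches no decision to the 45% bound, does not say whether it applies per arm or pooled, and states that the study is not powered to compare response. The figures for 40 and 80 assume that every randomized patient is dosed.

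**What to change.** Add two lines to the MR definition in Appendix C:

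1. Where serum and urine M-protein are unmeasurable, a 25–49% fall in the involved-minus-uninvolved FLC difference, on two determinations six weeks apart, replaces the M-protein lines.
2. Where a soft tissue plasmacytoma is the only measurable disease, a 25–49% reduction in its size, held for at least six weeks, qualifies.

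Eligibility and the cycle 4 rule stay as they are.

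**Cost.** The FLC line needs no new test. Freelite is scheduled on Day 1 of every cycle from cycle 2 (weeks 4, 8, 12 and 16), so a fall first seen at week 8 can be confirmed at week 16, when the decision falls due. Plasmacytoma measurements must be timed so that two, six weeks apart, precede that decision; footnote 7 of the schedule permits this but fixes no dates. The 25–49% bands are set by analogy with the M-protein band, which the clinical team should confirm. No additional marrow procedures are proposed.
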